10. DATA MANAGEMENT

Source data

All source data for this study will be maintained in the Electronic Medical Record system, in accordance with hospital regulatory and requirements for the protection of confidentiality of patients. The investigator will be responsible to ensure the accuracy and completeness of the data reported timely. Incoming data will be double checked to detect inconsistent or missing data. All related hard copies will be secured to ensure confidentiality. Access to the clinical information will be based on individuals' roles and responsibilities.

Investigator Records

Investigators will maintain complete and accurate records of this study, which will be maintained until two years after the date of the study completeness/termination. The following materials will be included in investigator records:

- (a) Correspondence: Documentation of all verbal and written correspondence with investigator, the Clinical Monitor, the Clinical Events Committee (CEC), and patients enrolled in this study.
- (b) Patient records: Signed informed consent forms and copies of all documents (medical records, laboratory reports, reports of diagnostic tests, etc.).
- (c) Clinical Study Protocol: A copy of the Clinical Study Protocol.
- (d) Ethics Committee (EC) Information: All information related to EC review and approval of this clinical study.
- (e) Other: Any other records that may be required.

11. QUALITY CONTROL AND QUALITY ASSURANCE

Protocol deviations

A protocol deviation is a failure to comply with the requirements of this clinical study protocol. Each investigator shall conduct this clinical study in compliance with this clinical study protocol, hospital regulations, ISO guidelines, Good Clinical Practices (GCP), and other study requirements.

The protocol deviations include, but not limited to the following:

- Failure to obtain patient's informed consent
- Failure to meet all of the inclusion/exclusion criteria
- Failure to conduct follow-ups required by this protocol

All deviations shall be assessed for the impact by investigators. Continued protocol deviations may result in termination of the study. The investigators reserve the right to terminate the study at any time.

Investigator and monitor training

The investigators and monitors will be trained appropriately to monitor study progress.

Clinical Events Committee (CEC)

An independent group of physicians that are not involved in the clinical investigations will act as the Clinical Events Committee (CEC), which will be responsible for the review and validation of reported potential adverse events. The CEC will be developed before the study start and blinded to the study details during the study period. This CEC shall include consistent definitions for each type of event and outline the review process.

Data and Safety Monitoring Board

To meet the study's ethical responsibility to its subjects, an independent data safety monitoring board (DSMB) will monitor the progress of the study. The board consists of physicians, biostatisticians, ethicists and bioengineers, who have no formal involvement or conflict of interest with the participants or the investigators. The DSMB will act in a senior advisory capacity regarding data and safety matters and review interim summary results of the accumulating data every 6 months. These data include adverse events (e.g., infection, bleeding, right heart failure) and mortality.

12. ANALYTICAL PLAN

Statistical overview

The aim of this study is to assess the safety and efficacy of our new operation (left atrial geometric volume reduction, pulmonary vein island isolation and left appendage base closure) in patients with MV disease and longstanding persistent AF. This study included a pilot study and a clinical trial, both of which are prospective, single-arm studies with similar statistical analysis plan.

Sample size

Sample size is based on previously published data, and on ensuring the ability to detect, with high probability, a clinically meaningful presumed benefit for our new operation. To date there have been some studies examining effect of COX MAZE IV in treating AF in MVS patients. The reported absence of AF one year post MVS with COX MAZE IV is about 60%-80%. For computing sample size, according to our pilot study, a reasonable proportion of patients free from AF at 1 year, will be assumed.

As observed in the pilot study that 20/20 (100%) patients free from AF at 6-month follow-up, we assume that 90% of patients treated with our new operation will be free of AF at 1-year post-surgery. A total of 120 patients enrolled in the clinical trial provides 80% power to detect an absolute increase of 10% (80% versus 90%) in the proportion of patients free of AF, based on a single-tailed 0.025 level continuity corrected chi-squared test and 10% drop-out rate. (ADDED at August 2018)

Primary analysis

The primary outcome of efficacy is freedom from AF over one year post surgery. The rate of free of AF will be calculated after finishing 1-year follow-up for 120 patients. Patients who die within 12 months will be considered treatment failures (not free of AF). Patients who die prior to the 12-month assessment, or who are determined by an independent adjudicator to be too ill to undergo AF measurement, will be considered as treatment failures (not free of AF). In the primary analysis, patients who undergo ablation therapy for AF (including surgical ablation or percutaneous catheter ablation) subsequent to the index procedure will be considered treatment failures (not free of AF). The primary safety endpoint of this trial include:

- (a) CPB time will be recorded.
- (b) a composite of death, stroke, serious cardiac events (heart failure, myocardial infarction), cardiac re-hospitalizations, transient ischemic attack, pulmonary embolism,

peripheral embolism, coronary artery injury, anatomical excessive bleeding, deep sternal wound infection/mediastinitis, damage to specialized conduction system requiring permanent pacemaker, and superior vena cava stenosis, within 30 days post-procedure or hospital discharge (whichever is later). The rate of these safety endpoints will be calculated within 30 days after surgery.

Secondary Analyses

Efficacy

(a) The size and shape of left atrium. The anteroposterior, transversal, and superoinferior diameters, as well as their ratios, of left atrium between two time points (i.e., before surgery and 12 months post-surgery), will be measured by transthoracic echocardiography. The absolute change and reduction rate of each diameter will be analyzed, and the post-surgery size and shape will be compared with Chinese standards.

(b) Left ventricular ejection fraction and peak late transmitral flow velocity (A) at 12 months post-surgery will be measured by transthoracic echocardiography. These measurements evaluate the function of heart pump.

Safety

(a) Major adverse cardiac events (MACE) defined as a non-weighted composite score of: death, stroke, worsening heart failure (+1 NYHA Class), CHF hospitalization, and mitral valve [MV] re-intervention within 12 months of surgery. The rate of MACE will be calculated and compared with MACE rate historically reported in COX MAZE IV procedure.

(b) Incidence of protocol-defined and serious adverse events (especially thromboembolic and hemorrhagic events) within 12 months of surgery. The rate of SAE will be calculated and compared with MACE rate historically reported in COX MAZE IV procedure.

(c) All-cause mortality at 12 months post-surgery. The Kaplan-Meier curve will be plotted to show the probability of death at a respective time interval and compared with 1-year deaths historically reported in COX MAZE IV procedure.

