4. OBJECTIVES

Primary objective

The primary objective is to assess the efficacy and safety of the new procedure (left atrial geometric volume reduction, pulmonary veins island isolation and left appendage base closure) for treating long standing persistent AF elimination. Efficacy will be evaluated by freedom from AF within 6 months and 12 months after surgery. Safety will be assessed by a composite of early adverse outcomes (within 30 days post-procedure or hospital discharge, whichever is later), including death, stroke, serious cardiac events (heart failure, myocardial infarction), cardiac re-hospitalizations, transient ischemic attack, pulmonary embolism, peripheral embolism, coronary artery injury, anatomical excessive bleeding, deep sternal wound infection/mediastinitis, damage to specialized conduction system requiring permanent pacemaker, and superior vena cava stenosis. We hypothesize that the new procedure will reduce the risk of AF post-MVS reoccurrence and lower the incidence of adverse outcomes, as compared to that was historically reported in patients undergoing MVS concomitantly with COX MAZE IV.

Secondary objectives

- (a) To assess the incidence of major adverse cardiac events and protocol-defined and serious adverse events (especially thromboembolic and hemorrhagic events) within 12 months after surgery, which is hypothesized to be lower than MVS concomitantly with COX MAZE IV.
- (b) To assess the intra-operation cardiopulmonary bypass time(CPB), which if prolonged could increase risk of poor prognosis within 30 days post-procedure or hospital discharge. CPB time is hypothesized to be shorter than that historically reported in COX MAZE IV procedure.
- (c) To assess the changes of size and shape of left atrium. The post-surgical shape and size of left atrium is hypothesized to be closer to normal status.
- (d) To assess the function of left atrium. The incidence of peak late trans-mitral flow velocity (A) at 12 months post-surgery is supposed to be high.

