5. STUDY DESIGN

This is a prospective, single-arm objective performance criteria study, consisting of two phases.

Phase I: A single-arm pilot study, 20 patients will be enrolled to test the feasibility of the procedure.

Phase II: A single-arm clinical trial, 120 patients will be enrolled to determine the safety and efficacy of the procedure.

Total study period is expected to take 40 months, and all patients will be followed for 12 months after surgery.

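### The 120-patient sample size gives 80% power only without a continuity correction; the corrected test the plan names has about 72% exact power (75.5% by normal approximation) at 108 evaluable

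*Combined protocol and SAP*

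**What the plan says.** All of the sample-size inputs stand in Section 12, Sample size. The alternative is stated as an assumption: "we assume that 90% of patients treated with our new operation will be free of AF at 1-year post-surgery". The null value of 80% is the upper end of the 60%-80% range that the same section gives for Cox-Maze IV. The claim is "A total of 120 patients enrolled in the clinical trial provides 80% power to detect an absolute increase of 10% (80% versus 90"%), and the test is specified as "based on a single-tailed 0.025 level continuity corrected chi-squared test and 10% drop-out rate".

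The design is one arm against a fixed criterion. Section 5 says "This is a prospective, single-arm objective performance criteria study, consisting of two phases". The primary hypothesis in Section 4 is framed "as compared to that was historically reported in patients undergoing MVS concomitantly with COX MAZE IV".

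The Primary analysis text in Section 12 says only "The rate of free of AF will be calculated after finishing 1-year follow-up for 120 patients". It gives no test against 80%, no confidence interval and no success threshold.

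**The concern.** The stated power and the named test do not appear to belong together. A continuity correction makes a one-sample test more conservative, so it needs more patients for the same power. If 120 came from the uncorrected formula, the trial has less than 80% power under the test that the plan names.

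The choice of rule can also decide the result. At 108 evaluable patients, 95 AF-free patients is a success under the uncorrected or exact binomial test and a failure under the corrected test. The only test named is in the Sample size paragraph, so the plan does not settle which rule governs the primary claim. In an open single-arm trial, that should be fixed before the outcome is known.

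**Working it through.** **Inputs (Section 12, Sample size; design from Section 5).** p0 = 0.80, p1 = 0.90, difference d = 0.10, one-sided alpha 0.025 (z = 1.960), power 80% (z = 0.8416), drop-out 10%, 120 enrolled. Evaluable: 120 × 0.9 = 108.

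**1. Reproducing the plan's figure, without correction.**

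n = [(1.960·√(0.8·0.2) + 0.8416·√(0.9·0.1)) / 0.10]² = [(0.7840 + 0.2525)/0.10]² = 107.43, so 108 evaluable.

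108/0.9 = 120.0, the stated number exactly. Approximate power at 108 is Φ[(√108·0.10 − 0.7840)/0.3] = Φ(0.851) = 80.3%.

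**2. With the correction the plan names.**

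n_c = (n/4)·[1 + √(1 + 2/(n·d))]² = (107.43/4)·[1 + √(1 + 2/10.743)]² = 117.21, so 118 evaluable.

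118/0.9 = 131.1, so 132 enrolled (131 if 117.21 is divided by 0.9 before rounding).

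Other readings with the correction also fail to give 120: one-sided 0.05 gives 103 enrolled, two-sided 0.025 gives 158, and a two-sample comparison needs 219 evaluable per arm.

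**3. Power of the named test at 108 evaluable.**

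- Normal approximation: Φ[(√108·0.10 − 0.7840 − 1/(2√108))/0.3] = Φ[(1.0392 − 0.7840 − 0.0481)/0.3] = Φ(0.690) = 75.5%.
- Critical count: 95 successes give (95 − 86.4 − 0.5)/√17.28 = 1.949, below 1.960, so 96 are needed.
- Exact: P(X ≥ 96 | 0.80) = 0.0105 and P(X ≥ 96 | 0.90) = 71.7%.

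**4. Exact binomial test at 108 evaluable.** The critical count is 95: P(X ≥ 95 | 0.80) = 0.0210 and P(X ≥ 95 | 0.90) = 81.0%. The Clopper-Pearson lower limit is 80.3% for 95/108 and 79.2% for 94/108.

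**5. Other numbers evaluable.** Exact power is saw-toothed in n:

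| Evaluable | Corrected test | Exact binomial test |
|---|---|---|
| 106 | 74.0% | 74.0% |
| 107 | 72.9% | 81.9% |
| 108 | 71.7% | 81.0% |
| 109 | 80.1% | 80.1% |
| 112 | 77.2% | 77.2% |
| 114 | 75.2% | 83.5% |
| 115 | 82.6% | 82.6% |
| 118 | 80.0% | 80.0% |
| 120 | 78.2% | 85.6% |

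Over 103-120 evaluable the corrected test runs from 71.7% to 82.6% and reaches 80% at five values of n (109 and 115-118). The exact test runs from 74.0% (n = 106) to 86.3% (n = 119), and its actual alpha is at most 0.0241.

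**6. Average exact power**, assuming each of the 120 patients is evaluable independently with probability q:

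| q | Corrected test | Exact binomial test |
|---|---|---|
| 0.85 | 72.6% | 75.8% |
| 0.90 | 75.7% | 78.8% |
| 0.95 | 78.8% | 81.6% |

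**7. Uncorrected test.** Its actual alpha exceeds 0.025 at some n: 0.0259 at 106, 0.0262 at 112, 0.0265 at 118.

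**The case against.** The best defence concerns size. The 71.7% is a low point of the saw-tooth: one more evaluable patient gives 80.1%. The plan's own power is an approximate figure, so the like-for-like comparison is 75.5% against 80.3%. At many values of n the corrected and exact tests have the same critical count and so the same power. Of the average shortfall of about 4 points (80% against 75.7%), about 3 come from the correction. The remaining 1 or so comes from discreteness and a random n, which the exact test shares (78.8%). All of this stands, and it limits the practical loss.

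The number analysed could also exceed 108. Deaths, patients too ill to assess and repeat ablations count as failures and stay in the denominator, so only true loss to follow-up reduces n. With all 120 analysed, the corrected test has 81.2% power by approximation but 78.2% exactly. That case uses none of the 10% drop-out the plan allows for, so it cannot support the stated calculation.

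One could simply delete the words for the correction. At 108 the uncorrected and exact tests are the same rule, and the uncorrected test's excess over 0.025 is small (at most 0.0015 at the values above). That would repair the arithmetic at 108. It would not hold alpha at every n, nor give the Primary analysis a decision rule.

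Finally, because only one test is named anywhere, it may be natural to assume that it applies. If so, the stated 80% is wrong for it.

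**Conclusion.** The concern holds. The number 120 is the result for an uncorrected one-sample test, while the plan names a corrected one. On the plan's own 10% drop-out, the named test has 75.5% power by normal approximation and 71.7% exactly, against a stated 80%. The loss averages about 4 points if 90% of patients are evaluable, and is smaller if retention is better.

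This rests on a one-sample reading, which the single-arm design requires, and on the plan's 80% and 90% rates. The averages also rest on the assumed evaluable probabilities. The corrected test is conservative, so what is at stake is lost power and an unclear decision rule, not a false-positive risk. It should be fixed, but it does not make 120 patients untenable: an exact binomial test has 81.0% power at 108.

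**What to change.** In both the Sample size and Primary analysis parts of Section 12, name one test: a one-sided exact binomial test of H0: p ≤ 80% at 0.025. Define success as a lower limit of the two-sided 95% Clopper-Pearson interval for the 12-month AF-free proportion above 80%, computed on whatever number is evaluable. Keep in the denominator the deaths, too-ill patients and repeat ablations that already count as failures. State power as 81% at exactly 108 evaluable (at least 95 successes, actual alpha 0.021), ranging from about 74% to 86% over 103-120 evaluable and averaging about 79% if 90% are evaluable.

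This is a wording change with no extra patients. It holds one-sided alpha at or below 0.025 at every n and gains about 3 points of power on average over the corrected test. It does not guarantee 80% at every n.

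If the corrected test is kept, restate its power at 108 evaluable as 75.5% by approximation and about 72% exactly. Restoring 80% by its own formula would need 132 enrolled in Phase II, 12 more. With the 20 pilot patients that makes 152, above the 140 maximum in the Study Summary, so that limit would have to change too.

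### The primary safety claims against historical Cox-Maze IV have no reference value, interval, test or criterion, and the efficacy test used for sample size is not carried into the primary analysis

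*Combined protocol and SAP*

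**What the plan says.** Section 5 states: "This is a prospective, single-arm objective performance criteria study, consisting of two phases". Section 4 makes safety part of the primary hypothesis: the procedure is expected to "lower the incidence of adverse outcomes, as compared to that was historically reported in patients undergoing MVS concomitantly with COX MAZE IV". The same section hypothesizes, under secondary objective (b), that CPB time will be shorter than historically reported for Cox-Maze IV. Sections 2, 8 and 12 list CPB time as a primary safety endpoint.

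Section 12 (Primary analysis) gives the whole planned analysis of these endpoints. CPB time is to be recorded. For the composite: "The rate of these safety endpoints will be calculated within 30 days after surgery". The sentence just before that defines the composite over 30 days or hospital discharge, whichever is later, so two windows stand side by side.

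For efficacy, the Sample size part of Section 12 cites historical freedom from AF of about 60% to 80%. It powers the trial for 80% versus 90%, "based on a single-tailed 0.025 level continuity corrected chi-squared test and 10% drop-out rate". The Primary analysis part then says: "The rate of free of AF will be calculated after finishing 1-year follow-up for 120 patients". It also lists who counts as a failure: patients who die, who are too ill to be assessed, or who have further ablation. It gives no interval, test or success rule.

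**The concern.** A performance-criteria design rests on a criterion fixed in advance that the result can miss. For primary safety there is none, so no observed composite rate or CPB time could contradict the hypothesis. The composite has about a dozen components and two windows. A reference chosen after the results are known could differ from it in components, window or population.

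The efficacy gap is narrower. A reference and a test exist, but only as the justification for the number of patients. Because history is quoted as a range, the text does not bind the analysis to its upper end.

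**Working it through.** **1. Reproduce the plan's figure.** Inputs from Section 12: p0 = 0.80, p1 = 0.90, one-sided 0.025, power 80%, drop-out 10%, N = 120.

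One-sample normal approximation without continuity correction:

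n = (1.960 × √(0.8 × 0.2) + 0.842 × √(0.9 × 0.1))² / 0.10² = 107.4, so 108; 108/0.9 = 120. This matches.

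With the continuity correction that the text names:

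n_cc = (n/4) × (1 + √(1 + 2/(n × 0.10)))² = 117.2, so 118; 118/0.9 = 131.1, so 132. This does not match.

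The 120 is therefore a one-sample comparison with 80%, computed without the stated correction.

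**2. The efficacy pass mark this implies.** The exact test passes at the smallest r with P(X ≥ r | n, 0.80) ≤ 0.025. The continuity-corrected test passes when (r − 0.5 − 0.8n)/√(0.16n) ≥ 1.960. Size and power below are exact binomial, with power taken at 90%.

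| Test | n | Pass mark | Actual size | Power |
|---|---|---|---|---|
| Exact | 120 | 105 (87.5%) | 0.0218 | 85.6% |
| Continuity-corrected | 120 | 106 (88.3%) | 0.0114 | 78.2% |
| Exact | 108 | 95 (88.0%) | 0.0210 | 81.0% |
| Continuity-corrected | 108 | 96 (88.9%) | 0.0105 | 71.7% |

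At 120, a count of 105 gives a corrected z of 1.94 and 106 gives 2.17.

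**3. Why the reference must be fixed.** Against 60%, the lower end of the quoted history, the exact test passes at 83/120 (69.2%; p = 0.024). Against 80% it needs 105/120. A result of 97/120 (80.8%) lies above 80% as a bare rate, yet its one-sided exact p is 0.46 and its exact 95% interval is 72.6% to 87.4%.

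**4. Why the denominator must be fixed.** The sample-size arithmetic removes drop-outs (120 × 0.9 = 108), but the analysis sentence refers to 120 patients. The plan does not say how patients with no 12-month assessment for other reasons are counted. If 12 such patients were counted as failures on 120, passing would need 105 of the remaining 108 (97.2%). If they were excluded, it would need 95 of 108.

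**5. Safety precision at 120 patients.** The documents give no safety rate, so the event counts are assumptions.

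| Events | Rate | Exact 95% interval |
|---|---|---|
| 6 | 5% | 1.9% to 10.6% |
| 12 | 10% | 5.3% to 16.8% |
| 18 | 15% | 9.1% to 22.7% |
| 24 | 20% | 13.3% to 28.3% |

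**6. What a safety claim would need.** The reference rate is again an assumption, shown as a range. The table uses an exact one-sided 0.025 test at n = 120.

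| Assumed reference | Most events allowing a claim of lower | Power if the true rate is half the reference | Power if it is 5 points below |
|---|---|---|---|
| 5% | 1 | 20% | not meaningful |
| 10% | 5 | 44% | 44% |
| 15% | 10 | 71% | 34% |
| 20% | 15 | 86% | 27% |
| 25% | 20 | 93% | 21% |
| 30% | 25 | 97% | 17% |

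No such calculation is possible for CPB time: the documents give no historical time and no standard deviation.

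**The case against.** The best defence concerns efficacy. A reader might infer that Section 12 contains no test at all, so that any observed rate of freedom from AF could count as success. The documents do not support that. The sample-size paragraph is part of Section 12 and gives a reference, a level, a direction and a named test. From these a pass mark of 106/120 can be derived, and 97/120 would fail it. What remains is that the Primary analysis text does not adopt the test or state an interval or success rule.

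A reader might also infer that the plan makes no historical comparison on safety. It does: Section 12 says that the 12-month MACE rate, serious adverse events and mortality will be compared with Cox-Maze IV reports. That stands, but it does not fill the primary gap. Those endpoints are secondary and cover 12 months. They carry no figures or method, and the serious adverse event rate is to be set against a historical MACE rate. The primary composite lacks even a stated comparison.

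Finally, the safety rates used above are illustrative. They show what 120 patients can resolve. They do not show an error in a planned figure or predict how results would be reported.

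**Conclusion.** The point holds in full for primary safety and in part for efficacy. The stated safety hypotheses, fewer early adverse outcomes and shorter CPB time, cannot be established by the analysis as written. Over assumed reference rates of 5% to 30%, the power of 120 patients to show a halving runs from 20% to 97%. Whether the claim is attainable therefore depends on a number that the plan does not give.

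For efficacy the defect is one of specification. The test exists but is not in the primary analysis, the reference is not bound to 80%, and the denominator is open. The named continuity-corrected test has about 78% power at 120 and 72% at 108 evaluable patients, against 86% and 81% for an exact test. These figures assume a true rate of 90%, as the plan does. The change should be made because it decides what the trial may conclude.

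**What to change.** **Safety.** Report the 30-day composite with an exact 95% confidence interval and CPB time with a 95% confidence interval. Reconcile the two composite windows in Section 12. Delete the claims of lower adverse outcomes and shorter CPB time from Section 4, unless a historical value is written down before data lock. For the composite, that value must have the same components and window. If a claim is kept, the upper confidence limit must lie below that value.

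**Efficacy.** State in the Primary analysis an exact one-sided 0.025 binomial test of 12-month freedom from AF against 80%, on one pre-stated denominator that covers patients with no assessment. Success requires the lower exact 95% limit to exceed 80%, which is at least 105/120 if all 120 are counted. Say explicitly that this replaces the continuity-corrected chi-squared test, which would need 106/120.

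**Cost.** A weaker safety claim, changed wording in Section 4, and a few more lines in Section 12. No extra patients or data.

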	
Safety: Major adverse cardiac events, which were defined as a non-weighted composite score of: death, stroke, worsening heart failure (+1 NYHA Class), hospitalization for heart failure, and mitral valve re-intervention within 12 months after surgery; and incidence of protocol-defined serious adverse events (especially thromboembolic and hemorrhagic events) within 12 months after surgery.

Follow-up Schedule	
Pre-discharge, and at 30 days, 3, 6, and 12 months after surgery.

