8. ENDPOINTS

Primary Endpoints

Efficacy

Freedom from AF in patients with longstanding persistent AF undergoing MVS at 6 months and 12 months. AF will be measured by 7 days continuous Holter monitoring at 6 months and 12 months post-surgery; and freedom of AF will be defined by absence of AF lasting > 30 seconds at 12 months.

Patients will be considered as treatment failures (not free of AF) if: 1) they die prior to the 12-month assessment; 2) or they are determined by an independent adjudicator to be too ill to undergo AF assessment; 3) or they require additional ablation therapy for AF (including surgical ablation or percutaneous catheter ablation) subsequent to the index procedure.

Safety

(a)Cardiopulmonary bypass time, which if prolonged could increase risk of poor prognosis within 30 days post-procedure or hospital discharge;

(b)The adverse events within 30 days after surgery, including: death, stroke, serious cardiac events (heart failure, myocardial infarction), cardiac re-hospitalizations, transient ischemic attack, pulmonary embolism, peripheral embolism, coronary artery injury, anatomical excessive bleeding, deep sternal wound infection/mediastinitis, damage to specialized conduction system requiring permanent pacemaker, and superior vena cava stenosis.

Secondary Endpoints

Efficacy

(a)The changes of size and shape of left atrium, which will be measured by comparing the anteroposterior, transversal, and superoinferior diameters of left atrium between 3 time points (i.e., before surgery, 6 months and 12 months post-surgery) by using transthoracic echocardiography.

(b)The peak late trans-mitral flow velocity (A) at 6 months and 12 months post-surgery, which will be measured by transthoracic echocardiography.

Safety

(a)MACEs within 12 months after surgery: defined as a non-weighted composite score

of: death, stroke, worsening heart failure (+1 NYHA Class), CHF hospitalization, and mitral valve [MV] re-intervention.

(b) Protocol-defined and serious cerebrovascular adverse events (especially thromboembolic and hemorrhagic events) within 12 months after surgery.

(c) All-cause mortality at 12 months after surgery.

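### Section 12 compares the 12-month serious adverse event rate with a historical Cox-Maze IV MACE rate, a different outcome, and the event scope is worded three ways

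*Combined protocol and SAP*

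**What the plan says.** Section 12, Secondary Analyses, Safety, has three items set against Cox-Maze IV history.

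- Item (a) defines MACE as a composite of "death, stroke, worsening heart failure (+1 NYHA Class), CHF hospitalization, and mitral valve [MV] re-intervention within 12 months of surgery", and then: "The rate of MACE will be calculated and compared with MACE rate historically reported in COX MAZE IV procedure".
- Item (b) is "Incidence of protocol-defined and serious adverse events (especially thromboembolic and hemorrhagic events) within 12 months of surgery", and then: "The rate of SAE will be calculated and compared with MACE rate historically reported in COX MAZE IV procedure".
- Item (c) sets 12-month mortality against historical one-year deaths.

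Item (b) serves secondary objective (a) in Section 4, which covers "the incidence of major adverse cardiac events and protocol-defined and serious adverse events (especially thromboembolic and hemorrhagic events) within 12 months". The objective then gives the expected direction for these outcomes: "which is hypothesized to be lower than MVS concomitantly with COX MAZE IV".

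The scope of the SAE endpoint has three wordings:

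- Section 2: "incidence of protocol-defined serious adverse events (especially thromboembolic and hemorrhagic events) within 12 months after surgery".
- Sections 4 and 12: the same phrase with an *and* between protocol-defined and serious, as quoted above.
- Section 8, Secondary Endpoints, Safety (b): protocol-defined and "serious cerebrovascular adverse events (especially thromboembolic and hemorrhagic events) within 12 months after surgery".

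Separately, the primary safety composite is counted to the later of 30 days or hospital discharge in Section 2, in Section 4 and in the Section 12 definition. It is counted to 30 days only in Section 8 and in the Section 12 sentence that directly follows the definition.

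**The concern.** An event rate can be judged against history only if the historical figure counts the same events over the same period. Items (a) and (c) meet that condition for the outcome; item (b) does not. Its text singles out thromboembolic and hemorrhagic events, yet apart from stroke neither is a named MACE component. Section 13 defines bleeding, arterial non-CNS thromboembolism and venous thromboembolism as events in their own right.

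This is a single-arm study, so an external rate is the only basis for the hypothesis that SAE incidence is lower than with Cox-Maze IV. As written, an observed difference could reflect the two definitions rather than the operation. Because the scope is unsettled, the direction of that artefact is also unsettled, and it could be fixed after the data are seen.

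**Working it through.** **No plan figure to reproduce.** The documents give no historical MACE or SAE rate, and no test, interval, alpha or decision rule for this comparison.

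**Step 1: direction under each reading of the scope.**

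- *Union (any protocol-defined event, plus any serious event).* Section 13 covers essentially every MACE component. Stroke is defined there, as is heart failure worsening by at least one NYHA class. The residual category, Other, takes in fatal events and those requiring hospitalization, and so in effect re-intervention. The SAE rate is then at least the trial's own MACE rate, and the comparison tends to work against the new operation.
- *Cerebrovascular only (one reading of Section 8).* MACE components other than stroke need not count. The SAE rate can fall below the MACE rate, which could flatter the operation. Section 8 can also be read as protocol-defined events plus serious cerebrovascular events, which is much broader.
- *Intersection (protocol-defined and also serious; the natural reading of Section 2 and a possible one of Sections 4 and 12).* A one-class NYHA worsening without hospitalization counts in MACE but need not be serious. This too could flatter the operation, without any cerebrovascular restriction.

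**Step 2: how many patients it takes.** Inputs: n = 120 (Phase II, Section 5); historical MACE rate p0 assumed at 5%, 10%, 15% or 20% and treated as known without error; the trial's MACE count set to p0 × 120, so that the operation is no better or worse than history on MACE; the exact (Clopper-Pearson) 95% interval as an assumed yardstick.

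Let s be the smallest number of patients with an SAE but no MACE for which the lower limit for (120·p0 + s)/120 exceeds p0. Let m be the smallest number of MACE patients who have no qualifying SAE for which the upper limit for (120·p0 − m)/120 is below p0. The second calculation assumes that no qualifying SAE occurs outside MACE.

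| p0 | MACE count | s | SAE count, 95% interval | m | SAE count, 95% interval |
|---|---|---|---|---|---|
| 5% | 6 | 6 | 12, 5.27–16.82% | 5 | 1, 0.02–4.56% |
| 10% | 12 | 8 | 20, 10.49–24.56% | 7 | 5, 1.37–9.46% |
| 15% | 18 | 9 | 27, 15.38–31.02% | 8 | 10, 4.07–14.79% |
| 20% | 24 | 10 | 34, 20.49–37.28% | 9 | 15, 7.17–19.78% |

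Broad scope: 6 to 10 patients, that is 6/120 = 5.0 to 10/120 = 8.3 percentage points, make the operation look worse. Narrow scope: 5 to 9 patients, that is 5/120 = 4.2 to 9/120 = 7.5 points, make it look better. The documents do not say how many such patients to expect.

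**Step 3: the primary safety window.** The two windows differ only for a patient whose first component event falls after day 30 and before discharge. Each such patient moves the composite rate by 1/120 = 0.83 points. The number of such patients is not given and may be zero.

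**The case against.** The strongest reply is that this is a drafting slip. The comparison sentence in item (b) repeats the one in item (a) with only the first outcome name changed. Items (a) and (c) compare like with like, and Section 4 sets each outcome against Cox-Maze IV, so the intent can probably be guessed. That stands as an explanation, and a reader should not infer that MACE was deliberately chosen as a convenient benchmark. It does not remove the point: no other section corrects the sentence, and an analyst who follows it makes an invalid comparison.

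Second, the patient counts above come from an assumed benchmark and an assumed yardstick. This also stands. They are thresholds under stated assumptions, not estimated effects. The narrow case also sets aside events such as transient ischemic attack, which Section 13 defines but MACE does not include; those would offset m. The figures are therefore best read as a net difference between the two definitions.

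Third, the scope variation should not be overstated. Four sections are involved but there are three wordings, since Sections 4 and 12 agree, and the most material difference is the single word *cerebrovascular* in Section 8.

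Fourth, the 30-day counting sentence in Section 12 may be shorthand for the definition just before it. That is possible, but Section 8 also says 30 days only.

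**Conclusion.** The point holds. The comparator in item (b) is wrong as written, and the SAE half of secondary objective (a) has no valid historical comparison. The MACE half is not affected by this point.

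A reader might infer that the error favours the new operation, or that only the cerebrovascular reading could do so. The documents support neither. A union reading works against the operation, while a cerebrovascular-only or an intersection reading could favour it. A reader might also infer that safety reporting or the main trial conclusion is compromised. That does not follow: the SAE rate is still calculated and can be reported, and neither the sample size nor the primary efficacy analysis uses this comparison.

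On size, the documents give none. Under the assumptions set out above, a net difference of about 5 to 10 of 120 patients between the definitions is enough for an apparent difference. The mismatch itself rests on the text alone and needs none of those assumptions.

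The window inconsistency is real but minor. It affects only the reported primary safety rate, since no pass/fail threshold depends on it.

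**What to change.** 1. Choose one SAE scope and use the same words in Sections 2, 4, 8 and 12. State whether events must be both protocol-defined and serious or either one, and whether the endpoint is limited to cerebrovascular events.
2. In Section 12, Safety (b), replace the historical MACE rate with a historical Cox-Maze IV rate for the same events over 12 months, and cite its source. Where no such rate exists, report the SAE rate with its exact 95% interval and make no comparison. Separate historical comparisons for thromboembolic and hemorrhagic events would be an optional addition.
3. Use one window for the primary safety composite in Sections 2, 4, 8 and 12. The later of 30 days or discharge is one option; it also counts in-hospital events after day 30.

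The cost is wording. No new patient data are needed: Section 9 has adverse events recorded as they occur in hospital, and follow-up runs to 12 months. The SAE comparison is lost where no matching historical rate can be found, and under the later-of window the primary safety rate may be slightly less favourable.
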